2.0 Study Objectives

Building on patient-focused ACT pilots in cancer,^{25, 33, 34} this NCI-funded pilot trial tests a novel, dyadic telephone-based ACT program for addressing both fatigue interference (i.e., fatigue's negative impact on activities, mood, and cognition) in advanced GI cancer patients and family caregiver burden. In order to enhance translation to geographically dispersed individuals and those with high symptom burden or functional impairments, we will deliver the intervention via phone. Advanced GI cancer patients with moderate to severe fatigue interference and their primary family caregivers with significant caregiving burden ($N=50$ dyads) will be randomized to six weekly 50-minute telephone sessions of either (1) ACT or (2) education/support. ACT includes acceptance and mindfulness meditation exercises, identification of personal values, and engagement in activities consistent with these values. Examples of dyadic intervention components include joint mindfulness practices and having each participant describe the other person's strengths and resources for goal achievement. Feasibility will be examined via accrual, attrition, and adherence rates, and acceptability will be evaluated using a mixed methods approach (qualitative and quantitative). Outcomes will be assessed at baseline, 2 weeks post-intervention, and 3 months post-intervention. Findings will inform an R01 application to conduct a large-scale RCT of intervention efficacy. The study objectives are:

2.1 Primary Objective: To evaluate the feasibility and acceptability of delivering telephone-based ACT to advanced GI cancer patients and their caregivers.

2.2 Secondary Objective: To test the effects of telephone-based ACT on patient fatigue interference and caregiver burden (primary outcomes) as well as patient sleep interference and patient and caregiver engagement in daily activities, progress in value-based living, psychological flexibility, and QoL (secondary outcomes).

Hypothesis: ACT will lead to improved primary and secondary outcomes as compared to education/support.

2.3 Exploratory Objective:

To explore the effects of telephone-based ACT on patient and caregiver physical and mental health service use (tertiary outcomes).

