5.0 Study Design

The study procedures are shown in **Table 1**. Advanced GI cancer patients and caregivers ($N = 50$ dyads) who meet eligibility criteria and provide informed consent will be randomized to receive either six weekly sessions of the ACT intervention or the education/support condition. Outcomes will be assessed via telephone at baseline and approximately 2 weeks and 3 months post-intervention within the timing windows outlined below.

Table 1

Timing	Procedure and person(s) responsible
At least 3 weeks after the patient's advanced GI cancer diagnosis	
(1) The research assistant will contact potentially eligible patients, screen patients for eligibility, and obtain informed consent, which can be done verbally over the phone or face to face in the outpatient clinics at the IU Simon Cancer Center or Eskenazi Health (see "recruitment process" below).
 
(2) The research assistant will contact potentially eligible caregivers, screen caregivers for eligibility, and obtain informed consent, which can be done verbally over the phone or face to face in the outpatient clinics at the IU Simon Cancer Center or Eskenazi Health (see "recruitment procedures" below). If the caregiver is not eligible or does not consent to participate, then the patient will be informed that s/he is not eligible for the study.

Target date = about 1 week after recruitment of the patient and caregiver. The baseline assessment can be completed up to 1 month after recruitment.	(3) Patients and caregivers who consent to participate will complete a 30- or 25-minute baseline assessment over the phone, respectively (see "interview procedures" below). The interview will be administered by a trained research assistant or a trained doctoral student in clinical psychology.
Sessions will occur approximately 1 week from each other, with the first session occurring about 1 week following the baseline assessment. Participants will have up to 12 weeks to complete the 6 sessions.	(4) Patients and caregivers will participate in six, 50-minute telephone-based sessions of ACT or education/support. Sessions will be administered by licensed mental health professionals who are supervised by the PI and [name] who are clinical psychologists.

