6.0 Enrollment/Randomization

Following baseline assessments, patient-caregiver dyads ($N = 50$) will be randomly assigned to the ACT intervention or education/support condition in a 1:1 ratio using a stratified block randomization scheme to balance the groups by patient performance status (Eastern Cooperative Oncology Group scores 0 or 1 vs. 2).^{48, 50} We will stratify randomization by performance status because the decision to provide chemotherapy and other cancer treatments is often based on performance status.⁵¹ Randomization will be performed using a SAS procedure routinely employed by the IU Biostatistics Department. The study statistician will create the randomization procedure, and the PI will inform study therapists of their assigned patients. Other members of the study team will remain blind to participants' group assignment. All patients will be registered with the Indiana University Cancer Center Clinical Trials Office. Applicable regulatory documents must be completed and on file prior to registration of any patients.

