Advanced patients and caregivers ($N = 50$ dyads) who are eligible and provide informed consent will complete individual phone assessments at baseline and approximately 2 weeks and 3 months following the final intervention session (see Table 1 in section 5.0 above for allowable assessment windows). The baseline assessment takes about 30 minutes for patients and 25 minutes for caregivers. Each follow-up assessment takes about 25 minutes for patients and 20 minutes for caregivers. Interviewers will be blind to study condition. Assessments will include questions regarding demographics, medical history, and primary and secondary outcomes. Participants will be provided with copies of response options via email or postal mail to facilitate survey completion (see Appendix E). Patients and caregivers in the ACT condition will also be invited to complete a 30-minute individual qualitative interview about intervention acceptability within approximately two weeks of the 2-week follow-up assessment. Each participant will receive \$40 in Target gift cards via postal mail for each completed assessment (baseline and 2-week and 3-month follow-ups) for a possible total of \$120 in gift cards (\$160 in gift cards for ACT participants only) for their time. There is no cost to study participants. If we cannot reach

a participant for an interview or phone session after several attempts, we will mail them a letter asking them to contact the study team (Appendix C). Table 2 below outlines the assessment schedule at baseline and the two follow-ups.

Table 2. Quantitative Measures						
Domain	Measure	# Items	Baseline	2-week follow-up	3-month follow-up	Administered to Patients (P) or Caregivers (C)
Sociodemographics	Sociodemographics	7-8	X			P, C
Medical comorbidity	Checklist of 8-9 conditions	8-9	X			P, C
Functional status	Patient-reported ECOG	1	X	X	X	P
Cancer information (e.g., date of diagnosis, cancer treatments)	Chart review	n/a	X	X	X	N/A
Intervention acceptability	Intervention acceptability scale	6		X		P, C
Primary patient outcome: fatigue interference	Fatigue interference subscale of FSI	7	X	X	X	P
Primary caregiver outcome: caregiving burden	12-item short-form of Zarit Burden Interview	12	X	X	X	C
Secondary outcomes:						
• Sleep interference	PROMIS short-form sleep-related impairment measure	8	X	X	X	P
• Engagement in daily activities	PROMIS short-form measure of ability to participate in social roles and activities	6	X	X	X	P, C

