10.0 Study Withdrawal/Discontinuation

Criteria for removal from the study are as follows:

- Observed severe cognitive impairment that renders continued participation in the study impossible, such as confusion or impaired ability to read or to provide accurate answers to the interviewer.
- The patient consents to participate in the study, but their family caregiver declines study participation or is not eligible for this study. The patient would no longer be eligible to participate in this study, as we are interested in examining data from patient-caregiver dyads.
- If the patient or caregiver is no longer able to participate in this study due to death or medical factors or decides to stop participation, then the other member of the dyad (patient or caregiver) will no longer be eligible to participate in this study.
- The participant expresses significant distress related to completion of the study (the PI will refer the participant to clinical services if needed).
- The participant provides verbal or written notification that she has decided to discontinue study participation.
- The participant does not follow the study rules (e.g., repeatedly does not answer the phone to complete a scheduled interview).
- Any other reason for which the principal investigator believes the participant should be withdrawn.

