11.0 Statistical Considerations

Aim 1. Feasibility and acceptability will be evaluated via descriptive statistics for accrual, attrition, and adherence as well as Likert-scale items assessing intervention helpfulness. We will judge this trial as feasible if: 1) $\geq 60\%$ of screened eligible dyads enroll in the study;²¹ and 2) $\geq 70\%$ of enrolled dyads complete 5-6 intervention sessions and all assessments. We will judge this trial as acceptable if $\geq 70\%$ of dyads rate ACT as moderately to extremely helpful (i.e., an average score ≥ 4 on 1 to 5 Likert scale items).

To analyze qualitative data on ACT's acceptability, we will use an immersion/crystallization approach.⁸⁰ Research questions guiding the analysis pertain to the perceived helpfulness of ACT components and their impact on functioning and well-being. Interviews will first be transcribed by a trained research assistant. Analysis of the interview data will consist of two phases: open and focused coding.^{80, 81} In the open coding phase, the analysts (Drs. [name], [name], and a Ph.D. student in clinical psychology) will independently label each line of data to reflect meanings or themes emerging from the text. This is done iteratively, combining, adding, or eliminating themes, until analysts agree on a set of emergent thematic categories (codes). In focused coding, codes derived in open coding are independently applied to all transcripts. Special attention will be paid to negative cases (i.e., data that may call initial observations or interpretations into question).⁸² Transcripts will be divided evenly among analysts, with every fourth transcript coded in common to maintain consistency in coding over time. Analysts will meet bi-weekly to compare commonly-coded transcripts. Discrepancies will be resolved by consensus. Atlas-ti software will facilitate coding, and qualitative results will inform intervention refinement.

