Statistical power. Although our analyses focus on effect sizes rather than statistical significance, we calculated power for comparing primary outcomes (patient fatigue interference and caregiver burden) between study groups. With a sample size of 34 patients and 34 caregivers at 2 weeks post-intervention (assuming 15% attrition), we will have 80% power ($\rho=.05$, two-tailed) to detect a large intervention effect ($d=.99$) on either primary outcome in a linear mixed model.⁸⁵ ACT had large effects on distress and QoL outcomes in late-stage ovarian cancer patients ($d=.89-1.69$) compared to CBT³³ and a medium effect ($d=-.59$) on fatigue interference compared to education/support in metastatic breast cancer patients with moderate-severe baseline fatigue interference.³⁴

Missing data. All data will be assessed for missingness and multiple imputation with 50 imputed samples will be used.⁸⁶ We will also compare participants and those who decline participation or withdraw on demographic and medical factors using t-tests and Chi-square analyses. Further, we will carefully track study participation and try to understand the reasons for dropout and missing data wherever possible. Identifying potential dropout and missing data mechanisms will allow us to incorporate those factors as auxiliary variables for multiple imputation as well as full information maximum likelihood estimation method assuming Missing at Random in our future Phase II trial.

Potential covariates. T-tests and chi-square analyses will be performed to identify any group differences in potential baseline covariates (e.g., demographic and medical variables), and if there are differences these variables will be used as covariates.

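### The 34 patients and 34 caregivers in the power statement do not follow from 50 randomized dyads and 15% attrition, which on the plain reading leaves 42 to 43

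*Combined protocol and SAP*

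**What the plan says.** Section 6.0 sets the sample size and allocation: "patient-caregiver dyads ($N = 50$) will be randomly assigned to the ACT intervention or education/support condition in a 1:1 ratio". Sections 2.0, 5.0 and 7.0 (Interview Procedures) give the same 50 dyads. Randomization follows the baseline assessment, so each arm should start with 25 dyads.

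The power paragraph of section 11.0 states: "With a sample size of 34 patients and 34 caregivers at 2 weeks post-intervention (assuming 15% attrition), we will have 80% power". The test is two-tailed at .05, the detectable effect is d = .99 on either primary outcome, and the model is a linear mixed model. The paragraph does not say whether the 15% applies to persons or to dyads, and it shows no step from 50 to 34.

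Two other provisions bear on the point. Section 10.0 says that if the patient or caregiver dies, becomes medically unable to take part or decides to stop, "then the other member of the dyad (patient or caregiver) will no longer be eligible to participate in this study". Aim 1 in section 11.0 makes feasibility depend in part on at least 70% "of enrolled dyads complete 5-6 intervention sessions and all assessments".

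**The concern.** The evaluable sample size and the attrition rate cannot both be right for the planned enrolment. The gap is 8 to 9 dyads on the plain reading, which is too large for rounding, and the loss implied by 34 of 50 is more than double the stated rate.

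Three things depend on it. The reported detectable effect cannot be checked against the trial's own N and attrition. Expected dropout also bears on the primary objective, "To evaluate the feasibility and acceptability of delivering telephone-based ACT to advanced GI cancer patients and their caregivers", because retention is one of the feasibility criteria. And section 2.0 says the findings will inform an application for a large-scale trial, for which a clear attrition assumption is a useful benchmark.

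**Working it through.** **Inputs.** 50 dyads, 1:1 (section 6.0); 15% attrition, 34 patients and 34 caregivers at 2 weeks, 80% power, two-sided .05, d = .99 (section 11.0; the .05 is printed with the symbol ρ and read here as the significance level); dyad withdrawal rule (section 10.0); 70% completion criterion (section 11.0, Aim 1).

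**Step 1: reproduce the plan's power figure.** Take a two-group comparison of means at one time point with SD 1 and no baseline adjustment, since the document gives no within-person correlation. The noncentrality is d / √(1/n₁ + 1/n₂) with n₁ + n₂ − 2 degrees of freedom. For 17 + 17, √(2/17) = 0.343 and 0.99 / 0.343 = 2.89 on 32 df, which gives 79.9% power. The detectable d at 80% power is 0.991. So 34, 80% and .99 are mutually consistent.

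**Step 2: apply the stated attrition to the stated N.**

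- 50 × 0.85 = 42.5, so 42 or 43 dyads.
- In reverse, 34 / 0.85 = 40 and 34 / 50 = 0.68, so 34 is a 15% loss from 40 dyads or a 32% loss from 50.

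**Step 3: test whether the dyad withdrawal rule explains the gap.** Assume 15% loss per person, with each loss removing the partner:

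- partners leave together: 50 × 0.85 = 42.5
- losses independent: 50 × 0.85² = 36.1
- no dyad loses both members: 50 × (1 − 0.30) = 35, or 17.5 per arm

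The third case is the extreme, and 35 is the minimum. It becomes 34 only if 17.5 is rounded down in each arm. To reach 34 otherwise, loss per person would have to be 1 − √0.68 = 17.5% (independent) or 0.32 / 2 = 16% (no overlap).

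**Step 4: effect on the power statement, same calculation as Step 1.**

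| Evaluable dyads | Reading of 15% | Detectable d at 80% power | Power at d = .99 |
|---|---|---|---|
| 34 (17+17) | as stated | 0.991 | 79.9% |
| 35 (17+18) | per person, no overlap | 0.976 | 81.1% |
| 36 (18+18) | per person, independent | 0.961 | 82.3% |
| 42 (21+21) | per dyad, rounded down | 0.886 | 87.9% |
| 43 (21+22) | per dyad, rounded up | 0.875 | 88.7% |

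At d = .59, the earlier breast cancer pilot result cited in the same paragraph, power is about 39% with 34 dyads and 46% with 42.

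**Step 5: compare with the feasibility criterion.** 0.70 × 50 = 35 dyads. If 34 of 50 were the real expectation, 68% retention at 2 weeks would already be one dyad short, before the 3-month assessment.

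**The case against.** The strongest reply is that little depends on the sentence. The primary objective is feasibility and acceptability. Aim 2 sets out to estimate effects rather than test them, and the power paragraph opens with the same caveat. The document does not derive N = 50 from this calculation, and if 15% per dyad is right the statement understates power. All of that stands. It limits the consequence but does not supply the missing step.

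A second reply is that the 15% may be per person. Under the dyad rule the gap then shrinks to one or two dyads and d moves only from .99 to .96–.98. That is fair as to size, but the text does not say so, and even the extreme version ends at 35.

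Third, the conflict with the 70% criterion arises only if 34 of 50 is a genuine forecast. The document does not say it is; the only rate it states is 15%. This link is therefore conditional. The 40-dyad origin is likewise an inference from exact arithmetic.

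Fourth, the plan cites a power tool whose settings are not shown, and it intends multiple imputation, so the analysed set need not equal the 2-week completers. The two-group calculation matches .99 closely, which makes it a reasonable guide, but the 0.89 is illustrative until the sponsor re-runs its own calculation.

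**Conclusion.** The concern holds. The evaluable numbers do not follow from 50 dyads and 15% attrition: the plain reading gives 42 to 43, and no reading of the withdrawal rule at 15% per person gives fewer than 35 without rounding down in each arm. The power calculation itself is correct for 34; the error lies in the sample size carried into it.

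The consequence is modest. On the per-dyad reading the detectable effect is about 0.88 to 0.89 instead of .99. On either reading the pilot has under 50% power at d = .59, so what it can conclude does not change. These figures assume equal allocation, a single-time-point comparison without baseline adjustment, and losses spread evenly across arms. The sentence should be corrected because a stated sample size and detectable effect cannot be traced to the stated inputs.

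**What to change.** Revise the power sentence in section 11.0 so that enrolled N, attrition and evaluable n agree. Say whether the 15% is per person or per dyad, given the section 10.0 rule, and then use whichever case applies:

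- **50 dyads and 15% per dyad are right:** state about 42 evaluable dyads (21 per arm) and a detectable d of about 0.89 at 80% power, confirmed by re-running the cited tool.
- **34 of 50 is really expected:** state 32% dyad attrition, and reconcile 68% retention with the 70% criterion under Aim 1.
- **34 was carried over from a 40-dyad plan:** say so and update it.
- **34 was reached in another way:** show the derivation.

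The cost is one sentence. Enrolment, the analysis and the success criteria need not change.

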12.0 Statistical Data Management

Primary data will be collected via phone interviews and stored electronically in passphrase protected files on the secure Psychology network drive accessed through an encrypted computer. Only IRB-approved members of the research team will have access to study files. The storage location will be backed up automatically every day. Paper files will be stored in a locked filing cabinet in a locked room in the PI's laboratory. Other data sources include data from medical records that will be stored in separate passphrase protected electronic files and merged with the primary data as needed. Quality assurance steps will include built in range checks. The following quality control methods will be used: 1) single data entry with two independent checks of the accuracy of every data point; and 2) discussion of any data entry questions with the PI.

13.0 Privacy/Confidentiality Issues

To protect against loss of confidentiality and anonymity, participant data will be identified only by a unique identification number assigned to each participant upon enrollment. Except for this unique identification number, no other identifying information will appear on the interview documents collected during the study. The master file linking the participant names with their identification numbers will be stored in a passphrase protected electronic file on a secure network drive. Unless required by law, no identifying information will be shared with individuals or organizations not affiliated with the study. Regarding individuals who are not eligible for this study or decline study participation, their screening information will be stored separately from identifying information (e.g., names) and will be kept for auditing purposes for 3 months before being destroyed.

Data will be housed on the secure departmental server in Excel and SPSS as well as in Oncore. The OnCore® database is a comprehensive, web-based, Clinical Trial Management System (CTMS) which utilizes an Oracle database. OnCore® was developed by Forte Research Systems, Inc. and is used by the IUSCC Clinical Trials Office and supported by the Indiana Clinical and Translational Sciences Institute (CTSI). OnCore® properly used is compliant with Title 21 CFR Part 11. OnCore® provides users secure access with unique IDs/passwords and restricts access by assigned roles, from any location, to record, manage, and report on data associated with the operation and conduct of clinical trials.

Furthermore, all study materials and data will be kept in locked file cabinets in a locked office and in passphrase protected electronic files on the secure departmental server. Only project members will have access to the files via encrypted computers. Participant identifiers will be removed from qualitative interview transcripts. Finally, once data collection has concluded, the master file linking participant names with identification numbers will be destroyed.

14.0 Follow-up and Record Retention

Data collection is expected to take place for up to 2 years. Data will be retained for a minimum of 7 years in accordance with Indiana State law. Data will be destroyed in the following manner: (1) paper will be shredded; (2) computer files will be deleted; and (3) audio-recording files will be deleted.

